6.3.1. Non-Responder Imputation (NRI)

For analysis of categorical efficacy and health outcomes variables, missing data will be imputed using an NRI method. Patients will be considered non-responders for the NRI analysis if they do not meet the categorical efficacy criteria or have missing clinical efficacy data at a time point of interest.

The NRI method may be used when the estimand of interest uses the composite strategy (FDA 2021) for handling intercurrent events. In this strategy, patients with any intercurrent events that lead to the permanent discontinuation of assigned study treatment are defined to have failed treatment for all subsequent time points.

In addition, patients who were not adequately assessed to determine if they meet the clinical requirements for response at the time point of interest are also considered to have failed treatment.

For any interim analyses that occur, patients who, based on their treatment start date, would not have completed the visit corresponding to the selected endpoint at the time of the database lock will not be included in the analysis of that endpoint. Patients who have discontinued or otherwise have missing data and would have otherwise completed that visit at the time of database lock will be counted as non-responders for the interim analysis.

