	24 hours. Responses are graded on a 6-point scale in which a score of 0 indicates the patient has no symptoms (that is, "none") and a score of 5 indicates that the patient's symptom(s) are "very severe."			
Nocturnal Stool	The Nocturnal Stool instrument is a single item asking the patient to record the number of stools they had during the night (or day, for shift workers) causing them to wake from sleep.	Nocturnal Stool Score	Calculated by averaging data from all available of Mocturnal Stool for a 7 day period as described in Appendix 1.	Missing if fewer than 4 available measurements in the relevant 7 days.
Fatigue NRS	CCI	Fatigue NRS Score	Calculated by averaging data from all available diary entries of Fatigue NRS for a 7 day period as described in Appendix 1.	Missing if fewer than 4 available measurements in the relevant 7 days.
Bristol Stool Scale	The Bristol Stool Scale is a single item that provides a pictoral and verbal description of stool consistency and form ranging from Type 1 (Hard Lumps) to Type 5 (Watery/liquid). An additional option provided was "6. Did not poop."	Bristol Stool Scale score	Calculated by using the worst value (ie, largest number from 1 to 5) from all available diary entries of Bristol Stool Scale for a 7-day period as described in Appendix 1. Responses of "Did not poop," will be counted as missing for that day.	Missing if fewer than 4 available measurements in the relevant 7 days.
		Loose Stool	Bristol Stool Scale score of 4 or 5.	Bristol Stool Scale score is missing
PUCAI	The PUCAI (Turner et al. 2007) is a clinician-administered, 6-item questionnaire that measures: abdominal pain; RB; stool	PUCAI Score	All items are answered as an average over the 'past 2 days'. A total disease activity score is calculated from 0 to 85, with	Missing if any component is missing.

Measure	Description	Variable	Derivation / Comment	Definition of Missing
	consistency; number of stools;		Severe: 65-85	
	nocturnal stools; and activity level		Moderate: 35-60	
	(see Appendix 7 of the protocol).		Mild: 10-30, and	
			None: <10.	
			The clinician will record the patient or	
			caregiver/legal guardian responses for the	
			PUCAI electronically as source data in the	
			tablet device at appropriate visits.	
		PUCAI clinical	PUCAI clinical remission is defined as a	Missing if any component is
		remission	PUCAI score of <10 points	missing.
		PUCAI clinical	PUCAI clinical response is defined as a	Missing if any component is

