Abbreviations: CFB change from baseline; CI = confidence interval; mBOCF = modified baseline observation carried forward; mITT = modified intent-to-treat; MMS = Modified Mayo Score; NRI = non-responder imputation; NRS = Numerical Rating Scale; PUCAI = Pediatric Ulcerative Colitis Activity Index; Q12W = every 12 weeks.

 Table AMBU.6.6.
 Description of Exploratory Efficacy/Health Outcomes Analyses

Measure	Variable	Analysis Method (Section 6.1.3)	Population (Section 6.1.1)	Time Point(s)
Mayo Score and components	Change from baseline in SF, RB, and Total Symptomatic Score	Descriptive statistics and 95% CI for mean with mBOCF and as observed.	mITT	At each scheduled visit
	Change from baseline in ES	Descriptive statistics and 95% CI for mean with mBOCF and as observed.	mITT	Weeks 12 and 52
	Time to first symptomatic response	Descriptive statistics and 95% CI for mean.	mITT	During Induction Period
	Time to first symptomatic remission	Descriptive statistics and 95% CI for mean.	mITT	During Induction Period
	MMS Alternative Clinical Remission	Proportion for each weight/treatment dose group along with the 95% 2-sided CI with NRI and as observed.	mITT	Weeks 12 and 52
CRP	CRP CFB	Descriptive statistics and 95% CI for mean with mBOCF and as observed.	mITT	Week 12 Week 52
Fecal calprotectin	Fecal calprotectin CFB	Descriptive statistics and 95% CI for mean with mBOCF and as observed.	mITT	Week 12 Week 52
PGIC	Mean PGIC Score	Descriptive statistics and 95% CI for mean as observed.	mITT	Week 4, Week 8, Week 12, and Week 52
PGRS	PGRS Score CFB	Descriptive statistics and 95% CI for mean with mBOCF and as observed.	mITT	At each scheduled visit.
Nocturnal Stool	Nocturnal Stool Score CFB	Descriptive statistics and 95% CI for mean with mBOCF and as observed.	mITT - In patients with a nocturnal stool score ≥1 at baseline	At each scheduled visit.
CCI				At each scheduled visit.
Bristol Stool Scale	Loose stool	Proportion for each weight/treatment dose group along with the 95% 2-sided CI with NRI and as observed	mITT, in patients with loose stool at baseline	At each scheduled visit.

		Analysis Method	Population	
Measure	Variable	(Section 6.1.3)	(Section 6.1.1)	Time Point(s)
EIMs	Resolution of Baseline EIMs	Proportion for each weight/treatment dose group along with the 95% 2-sided CI with NRI and as	mITT – in patients with EIMs at baseline	Weeks 12 and 52
		observed.		

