Appendix 1. Diary Calculations

Weekly summary measures of diary data will be created for each patient. The 7-day period associated with each week will be defined using a visit centric approach. The table below displays the interval for each week.

Week (Visit)	Start Day ^a	End Daya	
Screening	Max(Informed Consent Date, Week 0 Visit Date - 14)	Week 0 Visit Date – 8	
Baseline	Week 0 Visit Date – 7	Week 0 Visit Date – 1	
Week 2 (V3)	Max(Week 0 Visit Date, Week 2 Visit Date – 7)	Week 2 Visit Date – 1	
Week 4 (V4)	Max(Week 2 Visit Date, Week 4 Visit Date – 7)	Week 4 Visit Date – 1	
Week 8 (V5)	Max(Week 4 Visit Date, Week 8 Visit Date – 7)	Week 8 Visit Date – 1	
Week 12 (V6)	Max(Week 8 Visit Date, Week 12 Visit Date – 7)	Week 12 Visit Date – 1	
Continue the algorithm as above.			
Week 48 (V15)	Max(Week 44 Visit Date, Week 48 Visit Date – 7)	Week 48 Visit Date – 1	
Week 52 (V16)	Max(Week 48 Visit Date, Week 52 Visit Date – 7)	Week 52 Visit Date – 1	

a If End Day < Start Day, do not assign specified visit week. Visit date will be calculated by selecting the first date from the following list (ie, first in list order): (1) date of endoscopy preparation if endoscopy preparation was performed, (2) date of endoscopy if endoscopy was performed, (3) date of treatment if treatment was given,
 (4) office visit date if available, or (5) imputed date of visit center of the protocol-defined window for that visit.

For the Mayo SF and RB subscores, the most recent 3 nonmissing days of the 7-day period in the table above will be averaged and rounded to the nearest integer to calculate the weekly score for each patient. Patients with less than 3 measurements in the 7-day period will be considered missing.

All diary data collected on the following days will be excluded from any calculations:

- any day(s) of bowel preparation
- day after any day(s) of bowel preparation (will most often be associated with date of endoscopy)
- day of endoscopy
- day after endoscopy, and
- two days after endoscopy (patients will be answering questions in a 24-hour recall fashion, so two days following endoscopy, they may be reporting their patient-reported outcomes from the day after the endoscopy).

For the Bristol Stool Scale the worst (ie, maximum) of the available measures during the 7-period in the table above will be used to calculate a weekly score for each patient. If fewer than

4 days are available (ie, not missing), the patient will be considered to be missing data for that week.

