For all other diary measures, all available days of the 7 days will be averaged to calculate the weekly score for each patient. If fewer than 4 days are available (ie, not missing), the patient will be considered to be missing data for that week.

If multiple diary assessments on a single day are present, use the latest assessment.

Signature Page for VV-CLIN-028381 v1.0 $\,$

Approval	PPD	
	11-Aug-2022 18:14:	49 GMT+0000

Signature Page for VV-CLIN-028381 v1.0

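### The weekly Bristol Stool score is a maximum over 4 to 7 usable days, so a child with intermittent loose stools and fewer usable days at follow-up is more likely to be counted as improved with no change in stools

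*SAP*

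**What the plan says.** SAP Table AMBU.6.4 (Section 6.10.1) defines the weekly score as "Calculated by using the worst value (ie, largest number from 1 to 5) from all available diary entries of Bristol Stool Scale" in a 7-day period. Appendix 1 agrees: "For the Bristol Stool Scale the worst (ie, maximum) of the available measures during the 7-period in the table above will be used". The score is "Missing if fewer than 4 available measurements in the relevant 7 days", and "Responses of 'Did not poop,' will be counted as missing for that day". A score therefore rests on 4, 5, 6 or 7 usable days.

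Loose Stool is a "Bristol Stool Scale score of 4 or 5". Table AMBU.6.6 analyses it at each scheduled visit, with NRI and as observed, in "mITT, in patients with loose stool at baseline". The baseline row of Table AMBU.6.3 uses the same cut.

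The rest of the diary is handled differently. Appendix 1 says "For all other diary measures, all available days of the 7 days will be averaged", and the Mayo stool frequency and rectal bleeding subscores use the 3 most recent non-missing days. For the Bristol score, no text fixes the number of days, matches it between baseline and follow-up, or plans a sensitivity analysis by diary completeness.

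**The concern.** The maximum of some of a week's days can never exceed the maximum of the whole week. Every child in this analysis starts as loose. Losing usable days at follow-up, while keeping at least 4, can therefore only move a child towards not loose. Bristol is the only diary item that combines a maximum with a varying day count.

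Poor compliance is not required: a fully completed diary with some no-stool days also yields fewer usable days. The study has no comparator arm (SAP Section 6.2 plans no treatment comparisons), so the artefact cannot cancel between groups. At stake is whether a fall in the Loose Stool proportion over 52 weeks reflects stools or the number of days recorded.

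**Working it through.** The plan states no rate, power or completion figure for this endpoint, so there is no figure to reproduce.

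**Inputs.** From the SAP: maximum rule, 4 to 7 usable days, cut at type 4 or 5, restriction to baseline-loose children. Assumed: a daily chance p that a usable day is type 4 or 5, independent days, and missingness unrelated to stools.

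**Step 1, constant p.** P(Loose Stool on k days) = 1 − (1 − p)^k.

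| p | 7 days | 6 days | 5 days | 4 days | Gap, 7 vs 4 (points) |
|---|---|---|---|---|---|
| 0.1 | 52.2% | 46.9% | 41.0% | 34.4% | 17.8 |
| 0.2 | 79.0% | 73.8% | 67.2% | 59.0% | 20.0 |
| 0.3 | 91.8% | 88.2% | 83.2% | 76.0% | 15.8 |
| 0.4 | 97.2% | 95.3% | 92.2% | 87.0% | 10.2 |
| 0.5 | 99.2% | 98.4% | 96.9% | 93.8% | 5.5 |
| 0.7 | 99.98% | 99.93% | 99.76% | 99.19% | 0.8 |

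With q = 1 − p the gap is q^4 − q^7. It is largest where 4q³ = 7q⁶, that is q³ = 4/7, so p = 0.170. The maximum is q^4 × 3/7 = 0.474 × 0.429 = 0.203, or 20.3 points. Some apparent improvement occurs even with 7 days at both times (21.0% at p = 0.2); only the excess is due to the day count.

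**Step 2, one fixed week with no model for the stools.** If j of 7 days are loose and m randomly chosen days are usable, the chance that all loose days are missed is C(7 − j, m)/C(7, m). With j = 1 this is 14.3% (m = 6), 28.6% (m = 5) and 42.9% (m = 4). With m = 4 it is 14.3% for j = 2, 2.9% for j = 3, and 0 for j = 4 or more.

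**Step 3, children differ.** Take p from Beta(2,4) (assumed), 7 usable baseline days and unchanged disease. Then E[(1 − p)^n] = 20/((n + 4)(n + 5)), and the share classed loose at baseline is 1 − 20/132 = 0.8485. The chance of still being loose on k follow-up days is

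1 − [20/((k + 4)(k + 5)) − 20/((k + 11)(k + 12))]/0.8485.

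This gives 89.0% (k = 7), 86.3% (6), 82.5% (5) and 77.1% (4). The excess is 12.0 points for 7 to 4 days and 2.8 points for 7 to 6.

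**Step 4, adding NRI.** Same model, each follow-up day usable with chance c, and a missing week counted as failure (still loose). The failure rate is the sum over k = 4 to 7 of P(k) × the Step 3 value, plus P(k < 4), with k binomial(7, c). It is 89.0% (c = 100%), 87.0% (90%), 85.2% (80%), 84.9% (70%) and 86.7% (60%). The largest net fall in this set is 89.0 − 84.9 = 4.1 points, after which it shrinks. As observed, the fall is 4.3 points at c = 80% and 6.3 at 70%.

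**Step 5, candidate remedies.**
- Share of usable days that are loose: its expectation is p for any k. Among baseline-loose children in Step 3 it is (1/3 − 0.0233)/0.8485 = 0.365 at every k from 4 to 7, where 0.0233 = 20/132 − 20/156.
- Maximum over a fixed number of days: k is the same at both times, so the excess is 0.
- Loose week defined as at least half of usable days loose: still depends on k. At p = 0.2 it gives 18.1% on 4 days against 3.3% on 7. In the Step 3 model, with children selected by that rule, 68% remain loose on 4 days and 53% on 7, a 15-point artefact.

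**The case against.** The strongest reply is about size and direction.

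- **Size.** Twenty points is close to the worst case and needs every child to go from 7 usable days to 4. Children enrolled have moderately to severely active disease and must be loose at baseline, so many may have loose stools on most days, where the gap is small. This stands, although no document gives p in either direction.
- **NRI.** SAP Section 6.3.1 says "Patients will be considered non-responders for the NRI analysis if they do not meet the categorical efficacy criteria or have missing clinical efficacy data", so weeks with fewer than 4 days add failures and partly offset the effect. This stands for the NRI analysis, with a caveat: the analysed variable is an unfavourable state, and the SAP does not say which Loose Stool value a missing week receives. The as-observed analysis has no such offset.
- **Direction.** A reader might infer that diary completion falls over 52 weeks and that the endpoint is therefore biased towards benefit. The documents do not support that. They give no completion rates, and the Protocol's Schedule of Activities reviews diary compliance at every treatment visit. Baseline could be the shorter week; the artefact would then run the other way.
- **Definition.** Any loose day in the week is a legitimate strict criterion. That is so, but it needs the same number of days at each visit to be comparable over time.
- **Weight.** The endpoint is exploratory and descriptive, in a subset of about 30 children. The primary PK, MMS and PUCAI endpoints are unaffected.

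**Conclusion.** The dependence on day count is real and nothing in the SAP corrects it. With fewer usable days at follow-up than at baseline, a child with intermittent loose stools is more likely to be counted as improved although nothing has changed. For 4 against 7 days the excess peaks at about 20 points (p near 0.17), is 5.5 points at p = 0.5 and is under 1 point at p of 0.7 or more. Under the assumed Beta(2,4) model with random missing days, the net effect after NRI is about 4 points. These sizes rest on an assumed p, independent days and missingness unrelated to stools.

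It would go too far to say that any child with fewer diary days looks improved. The effect is a matter of chance, disappears when four or more days of the week are loose, and requires fewer usable days at follow-up than at baseline. The importance is minor to low-moderate: worth correcting because the change is cheap, but confined to one exploratory endpoint.

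**What to change.** In SAP Tables AMBU.6.4 and AMBU.6.6 and Appendix 1, summarise the share of usable days with type 4 or 5 as a continuous weekly value, or use the daily mean as for the other diary items. Make the baseline row of Table AMBU.6.3 consistent.

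If a binary Loose Stool variable is kept, compute it over a fixed number of days at both baseline and follow-up, for example the most recent 4 usable days, in line with the 3-day Mayo rule. State which value NRI gives to a missing week. Do not define it as at least half of the usable days, which also depends on the count (Step 5).

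Tabulate usable days by visit, and keep the worst-of-week version as supportive.

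The cost is SAP wording and minor reprogramming, with no new data collection. The downside is a departure from the SAP's worst-value definition.
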